The study will enroll approximately 116 subjects from approximately 10 – 20 study centers in the United States. Subjects scheduled for urological or gynecological surgical procedures, age 18 to 85 years inclusive, will be screened for participation. Screening will occur within 30 days before study drug administration (Day of Surgery). After signing the informed consent, medical history, physical examination, baseline laboratory testing, pregnancy testing, 12-lead ECG, and vital sign measurements will be completed during the screening visit. Any procedure done for the purpose of the surgery before the date of signing the informed consent may be used as long as it was within 30 days of the scheduled surgery date.

On the day of surgery (Day 1) the subject will be evaluated for eligibility for randomization. Eligible subjects will be randomized to receive a dose of either IC high dose (5 mL) or IC low dose (2.5 mL). Each randomized subject will serve as his/her own control by receiving a dose of normal saline prior to receiving the randomized IC dose. The surgeon will be blinded to the IC dose a subject receives. Time of injection of saline and IC will be captured.

To evaluate the efficacy outcomes, each subject will first be injected intravenously with 5 mL 0.9% saline. The ureteral orifices/flow will be observed and video recorded for 10 mins. The time period that will be captured on video is from injection to 10 minutes post injection. If both ureters cannot be visualized simultaneously, then alternating 15-30 second images of each ureter or ureteral orifice will be obtained. The process will be repeated in the same patient for the IC dose. Hence, each subject will have 2 videos and each will be about 10 minutes in length.

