3.2. Interim Analysis

A formal interim analysis is planned in Protocol Amendment 2. Patient enrollment was paused while the conspicuity score criteria was developed. A total of 21 patients were randomized and treated at the time of enrollment pause. Since the study total sample size of approximately 116 patients to be enrolled will remain unchanged for the protocol amendment, and that the 21 subjects enrolled prior to 5-point conspicuity score is developed will be excluded from the final efficacy analysis (see Section 3.3), the timing of this planned interim analysis will be based on the enrollment of the remaining approximately 95 subjects. That is, this formal interim analysis is to be conducted when approximately 50% of the remaining patients are randomized and treated (approximately 47-48 patients). The objective of this interim analysis is to confirm the observed treatment effect size on the conspicuity score from the test dataset. The interim analysis will only analyze the conspicuity score provided by the central reviewers.

Since randomization to the IC dose level will not be unblinded during the interim analysis, the overall IC treatment effect will be analyzed using the proportional odds model; the model will include the main effect of treatment (IC vs Saline) and ureter (left vs right) and control for the repeated measures within a subject. This model is identical to the reduced model (Model 2) in the primary analysis of the primary endpoint described in **Section 5.1**.

Conditional Power (CP) will be calculated based on estimated odds ratio and corresponding standard error in log scale from the interim analysis data based on equation from Lan and Wittes

(1988) as summarized by professor Gary Kock in 2003 at Drug Information Association (DIA) 10th Annual Biostatistics Workshop in Japan, August 29, 2003 in Tokyo, Japan¹.

The prediction of the conditional power for a statistically significant result from the final analysis (at the two-sided 0.05 level) given the observed difference between treatments at a formal interim analysis can be based on the estimated treatment effect (equation 2); 2-sided 95% confidence intervals for the CP will also be calculated.

2. Estimated conditional power if the observed treatment difference at the interim analysis applies to the remainder of the study

$$\text{ProbNorm} \left\{ \left[\sqrt{\frac{(1-P)}{P}} + \sqrt{\frac{P}{(1-P)}} \right] Z - \frac{Z_\alpha}{\sqrt{1-P}} \right\}$$

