3.3. Analysis Population

The following analysis sets will be identified for this study.

Enrolled Analysis Set: All subjects who sign the ICF for the study are considered to have enrolled.

Intent-to-Treat (ITT) Analysis Set: The ITT Analysis Set will include all randomized subjects. This dataset may also be referenced as the 'Randomized Set'. The ITT subjects may or may not receive randomized treatment. All ITT subjects will be included in the randomized treatment group even if a dosing error occurred. See additional discussion in [Section 3.7](#).

Safety Analysis Set: The safety set will include all ITT Analysis Set subjects who are treated with any study drug (Saline or IC) and will be used for safety and tolerability assessments. In the safety analysis set all subjects will be included in the actual treatment group received if a dosing error occurred. See additional discussion in [Section 3.7](#).

Efficacy Analysis Set: The efficacy analysis set includes all Safety Analysis Set subjects who have a surgical procedure to assess ureteral patency and who have received both study drugs (Saline and IC dose) and a video approximately 10 minutes in length is available after each treatment. **The 21 patients who were randomized and treated prior to the development of the conspicuity score will be excluded from the efficacy population.** This will be the primary population for efficacy assessments. This is also referenced as the modified intent-to-treat (mITT) Analysis Set. All efficacy evaluations will be based on the mITT population. In the mITT analysis set all subjects will be included in the actual treatment group received if a dosing error occurred. See additional discussion in [Section 3.7](#).

Per Protocol (PP) Analysis Set: The PP set includes all subjects from the Efficacy Analysis Set who did not have any major protocol deviation that may confound the interpretation of the efficacy assessment. This Analysis Set will serve as a confirmation analysis set for efficacy analysis. In the PP analysis set all subjects will be included in the actual treatment group received if a dosing error occurred. See additional discussion in [Section 3.7](#).

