3.7. Treatment Group vs Randomization Group

All qualified subjects will be randomized to either a dose of 2.5 mL IC (referred to as the Low dose) or a dose of 5.0 mL IC (referred to as the High dose). All randomized subjects will receive a dose of normal saline before receiving the randomized IC dose.

Hence, there are 2 randomization groups, namely IC High Dose and IC Low Dose and 3 treatment groups (IC High dose, IC Low dose, and Saline) in this study.

If a dosing error occurred (e.g., a subject was randomized to the IC High dose but actually received IC Low dose, and vice versa), the subject will be included in the actual treatment group received for efficacy, PK, and safety analyses; this will be an important protocol deviation and the incident will be clearly documented in the study report and in the database.

Data presentation for study population, physician overall satisfaction, safety lab, and 12-ECG will be based on the 2 randomization groups; whereas the data presentation for conspicuity, TTV, adverse events, and vital signs will be based on the 3 treatment groups. A Study Overall group may be included in certain data presentations (e.g., demographics) if data warrant. The Saline group will include all subjects who had saline dose, hence, the number of subjects in this treatment group will expect to be twice the size of IC Low dose and IC High dose. If data warrants, the Saline group may also be split by IC dose group. That is, subjects received the IC Low dose vs subjects received the IC High dose.

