5.2. PSAS with IC Treatment

Each subject will have 1 PSAS score. Ratings in the PSAS with the IC treatment will be tabulated (**Table 14.2.2**) by treatment (IC High dose, IC Low dose, and overall (pooled across high dose and low dose) with number (%) subjects in each rating category and overall satisfactory.

Two-sided 95% confidence intervals on proportion of physicians who are satisfied (with ratings 1 or 2) will be derived using the Wilson confidence limits for the binomial proportion. This is also known as score confidence limits. The Wilson interval has been shown to have better performance than the Wald interval and the exact (Clopper-Pearson) interval (SAS Users' manual).

A binomial 1-way proportion approach will be used to examine that $\geq 50\%$ of the physicians are satisfied with the IC treatment (a superiority test) as an aid for the assessment of ureter patency comparing to the saline treatment. Below is an example of SAS syntax to implement this analysis.

```
DATA psas;
  Set PSASscore;
  If score in (1, 2) then psasC='1Yes'; else psasC='2No';
Run;
PROC SORT data=psas; BY trt psasC;
PROC FREQ DATA=psas ORDER=DATA;
  TABLES psasC / BINOMIAL(SUP P=0.45 MARGIN=0.05 CL=WILSON) alpha=.05;
  BY trt;
  ODS OUTPUT BinomialCLs=bCL
    BinomialSup=pval
  ;
run;
```

This syntax makes the 'Yes' response to be the first category so the binomial test will examine the proportion of response in the Yes category. The null proportion of 0.45 and margin of 0.05 makes the point estimate of superiority limit to be 0.50 (superiority limit = the null proportion + margin). The 'TRT' is coded to 'High', 'Low' or 'All'. 'All' includes subjects from both IC High and IC Low doses.

An exploratory analysis to examine any difference in PSAS with the use of IC High dose vs the IC Low dose will be performed via a Cochran-Mantel-Haenszel (CMH) test for 'Row Mean Scores Differ'. Below is an example of SAS syntax to implement this analysis

```
PROC FREQ DATA=psas;
  TABLES dose*psas / noproct CMH2 alpha=.05;
  ODS OUTPUT CMH=pval
  ;
run;
```

where 'dose' is coded to Low or High; the 'PSAS' is the satisfaction rating score (1, 2, 3, 4, or 5).

Normal p-value for each analysis will be reported as is without controlling for multiple comparisons.

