5.3. IC Treatment Responders

In this study each subject is served as his/her control when the IC treatment is given as a visualization aid when determining ureter patency, IC treatment responder, hence, could be defined based on the conspicuity score following IC and saline.

To determine proportion of subjects meeting the responder definition in conspicuity score following IC treatment the blinded central reviewer's assessment will be used. A subject is a responder when there is ≥ 1 point improvement in the conspicuity scores following the IC vs saline treatment (IC – Saline ≥ 1) and the conspicuity score following the IC treatment is (3, 4, or 5). The responder criteria will be assessed separately for each ureter for each subject.

Since the responder definition will be defined for each ureter per subject, when a subject has missing data, the corresponding responder variable cannot be defined. The primary analysis will exclude all subjects that the responder definition cannot be derived due to missing data; this will be referred to as the Observed Analysis.

To assess the impact of missing data, a sensitivity analysis will be conducted. In this sensitivity analysis, the responder variable will be set to 'No' for those that cannot be derived due to missing data. This analysis will represent the worst-case scenario for this analysis.

Summary tables (Tables 14.2.3.1 and 14.2.3.2) will provide number (%) subjects meeting the responder definition in the following categories: overall (left or right), left ureter, right ureter, or both ureters for each IC dose and overall; 95% confidence intervals based on normal approximation will also be provided, along with the difference in proportion of responders between the IC high dose vs IC low dose.

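### The responder proportions in SAP 5.3 get normal-approximation intervals although SAP 5.2 prefers Wilson; at about 47 subjects per dose their average coverage is below 95%, and they break down if responder rates are very high

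*SAP*

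**What the plan says.** SAP Section 5.3 tabulates the number and percentage of responders in four categories (left or right ureter, left, right, both), for each IC dose and for the doses together. For these it states that "95% confidence intervals based on normal approximation will also be provided". It also reports the High versus Low difference in proportions, without saying clearly whether that difference gets an interval. It gives no program code and no fallback for an observed 0% or 100%.

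SAP Section 5.2 treats the proportion of satisfied physicians, also one yes/no result per subject by dose and pooled. There the 95% limits "will be derived using the Wilson confidence limits for the binomial proportion", and the stated reason is: "The Wilson interval has been shown to have better performance than the Wald interval and the exact (Clopper-Pearson) interval".

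The sample size comes from three places. Section 2: "The study will enroll approximately 116 subjects". Section 3.3: "The 21 patients who were randomized and treated prior to the development of the conspicuity score will be excluded from the efficacy population". Section 3.2: "the timing of this planned interim analysis will be based on the enrollment of the remaining approximately 95 subjects". No section in the public text states an allocation ratio, but Section 3.7 says of the saline group that "the number of subjects in this treatment group will expect to be twice the size of IC Low dose and IC High dose", which implies 1:1.

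**The concern.** Two adjacent sections give intervals for the same kind of quantity, in the same analysis set, by two methods. The later section uses the one that the earlier section ranks lower, and gives no reason.

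The normal-approximation (Wald) interval is centred on the observed proportion and takes its width from it. In samples of this size its true coverage tends to fall below the nominal level, and the problem grows as the proportion nears 0 or 1. At exactly 100% the estimated standard error is zero, so the interval has no width.

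At stake is the honesty of the 95% label on a named secondary efficacy endpoint. The lower limit matters most, because a reader uses it to judge how low the true responder rate could be.

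**Working it through.** **Inputs**
- Efficacy set: 116 − 21 = 95, which reproduces the figure in SAP 3.2.
- Per dose: 95 / 2 = 47.5, so 47 or 48 under the inferred 1:1 split. Section 5.3 drops subjects whose responder status cannot be derived, so n may be smaller. (The 47–48 patients named in SAP 3.2 are the interim total, not the per-dose number.)
- z = 1.96.
- True responder rate: none is visible in the documents, and the sample-size assumptions are redacted. A range of 0.60 to 0.98 is assumed.
- Normal approximation is read in its usual sense, as Wald.

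**Formulas**, with p = x/n:
- Wald: p ± z·√(p(1−p)/n)
- Wilson: [p + z²/(2n) ± z·√(p(1−p)/n + z²/(4n²))] / (1 + z²/n)
- Exact coverage at true rate π: the sum of Binomial(x; n, π) over all x whose interval contains π. This is then averaged over a fine grid of π.

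**Mean exact coverage**

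| True rate | Wald, n = 47 | Wilson, n = 47 | Wald, n = 95 |
|---|---|---|---|
| 0.60–0.80 | 93.6% | 95.1% | 94.3% |
| 0.80–0.90 | 91.9% | 95.3% | 93.5% |
| 0.90–0.98 | 85.9% | 95.7% | 90.9% |

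Coverage oscillates with π. At n = 47, Wald covers 94.8% at 0.60, 94.4% at 0.70, 91.2% at 0.80, 95.0% at 0.90, 90.8% at 0.95, 75.8% at 0.97 and 61.3% at 0.98.

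**Intervals at n = 47**

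| Responders | Wald | Width | Wilson | Width |
|---|---|---|---|---|
| 28 (60%) | 45.5% to 73.6% | 0.281 | 45.3% to 72.4% | 0.270 |
| 37 (79%) | 67.0% to 90.4% | 0.234 | 65.1% to 88.0% | 0.229 |
| 42 (89%) | 80.5% to 98.2% | 0.176 | 77.4% to 95.4% | 0.180 |
| 45 (96%) | 90.0% to 101.5% | 0.115 | 85.8% to 98.8% | 0.131 |
| 46 (98%) | 93.7% to 102.0% | 0.083 | 88.9% to 99.6% | 0.107 |
| 47 (100%) | 100% to 100% | 0 | 92.4% to 100% | 0.076 |

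- Worked example, 46/47: p = 0.9787, standard error √(0.9787 × 0.0213 / 47) = 0.0210, half-width 0.0413, so 0.937 to 1.020.
- Worked example, 47/47: the Wilson lower limit reduces to n/(n + z²) = 47/50.84 = 0.924.
- The Wald upper limit exceeds 100% at 44, 45 and 46 of 47.
- Wald is narrower than Wilson only from 41/47 (87%) upward. Below that, down to about 50%, it is slightly wider, and its shortfall comes from centring on the raw proportion.

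**How likely is an all-responder dose group?** The chance of 47/47 is π^47: 0.05% at 0.85, 0.7% at 0.90, 9.0% at 0.95 and 23.9% at 0.97.

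**The case against.** The strongest reply is that little depends on these intervals. SAP 3.4 confines type I error control to the primary endpoint, and Section 5.3 sets no threshold or test, whereas the satisfaction endpoint in 5.2 is tested against 50%. The tables also show counts, so a reader who sees 47 of 47 can compute any interval. All of this stands and limits the consequence. It is not a reason to keep the method that the SAP itself ranks lower.

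Three stronger readings are tempting, and the documents do not support them.
- *That the intervals are generally too narrow.* At n = 47 this holds only at observed rates of about 87% or more.
- *That responder rates will be near 100%, so severe failure is to be expected.* SAP 3.1 says only that IC should do better than saline. A responder needs a gain of at least one point and an IC score of 3 to 5, and under the scale in Section 2 a saline jet can already score 3 for significant flow. Superiority to saline therefore does not imply rates near 100%. At some moderate rates Wald coverage is close to nominal.
- *That the High versus Low comparison is compromised.* Section 5.3 does not clearly promise an interval for the difference. If a Wald one were given with 47 and 48 subjects, its exact coverage is 94.6% at true rates 0.95/0.90, 94.3% at 0.90/0.80 and 94.4% at 0.70/0.60. It drops to 90.3% at 0.97/0.95, where Newcombe over-covers at 98.6%.

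**Conclusion.** The inconsistency between Sections 5.2 and 5.3 is real and worth correcting. At the per-dose sample size, average Wald coverage is below 95% in every range of responder rate examined: by about 1.4 points for 0.60–0.80, 3.1 for 0.80–0.90 and 9.1 for 0.90–0.98. Wilson averages at or just above 95% throughout, so the case for changing does not rest on rates near 100%. Pooling the doses halves the shortfall or better in the two lower ranges, but leaves about 4 points in the highest.

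Limits above 100% and a zero-width interval are possible rather than predicted. They need observed rates of about 94% (44/47) or more.

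The conclusion assumes 1:1 allocation, about 47 subjects per dose, Wald as the meaning of normal approximation, and an assumed range of rates because none is visible. It concerns the reporting of a descriptive secondary endpoint. The primary analysis is unaffected.

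**What to change.** In SAP Section 5.3, and in Tables 14.2.3.1 and 14.2.3.2, replace the normal-approximation intervals with two-sided 95% Wilson score limits, as in Section 5.2, for every single proportion (each ureter category, each dose and pooled). State whether the IC High minus IC Low difference gets an interval. If it does, the Newcombe interval built from Wilson limits is the consistent choice.

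The cost is one sentence in the SAP and one program option that already appears in the code of Section 5.2. The trade-off is that intervals near 100% become wider and their lower limits less favourable, for example 88.9% in place of 93.7% at 46 of 47.

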5.4. Time to Visualization

In this study each subject will contribute 2 TTV observations, one for left and one for right ureter. Each time to event observation will be considered an independent observation.

As indicated earlier in [Section 3.7](#) the summary table for this endpoint will include 2 treatment groups, namely IC High Dose, IC Low Dose. Time (minutes) to visualization (TTV) of blue color in the ureter jet flow will be evaluated using the Kaplan-Meier Survival Analysis approach. Descriptive summary, including number of subjects (%) subjects censored; time to event percent-tiles (25%, 50%, and 75%) and 95% confidence intervals and Kaplan-Meier mean (SE) will be estimated for each ureter. The following is an example SAS syntax for this analysis.

```
ods output CensoredSummary=Ncensor
      ProductLimitEstimates=PL
      Means=KMmeans
      Quartiles=quart
      Survivalplot=SurvivalPlotData
      ;

PROC LIFETEST DATA=ttv METHOD=PL ATRISK
  PLOTS=survival(ATRISK(ATRISKTICK)= 0 2 4 6 8 10);
  TIME aval*Cnsr(1);
  *---- stratified test ---*;
  STRATA ureter / GROUP=trt;
  ;
run;
where TRT is coded to HighDose vs LowDose
```

In additional, KM-survival analysis descriptive summary will also be provided for the overall. In this analysis, number of observations will not be the same as number of subjects.

Using data ‘SurvivalPlotData’ Kaplan-Meier survival curves will be presented for each treatment group along with number of subjects at risk at 0, 2, 4, 6, 8, and 10 minutes. The KM-survival plots will be prepared for each ureter and overall.

If data warrants, a Cox Proportional hazards (PH) model will be fitted to estimate hazards ratios (HR) between IC High dose vs IC Low dose using a stratified Cox PH model that includes main effect of treatment and stratified by ureter (left vs right). The HR estimate and 95% CI for the HR will be based on the Score Statistics. The p-value for treatment effect will be based on the Score Statistics because the p-value from the score statistics produced by PROC PHREG will be the same as the stratified log-rank test produced by PROC LIFETEST. In order to obtain HR 95% CI using the score statistics, an external SAS macro developed by based on Lin (2016)⁴ will be used (because the current SAS 9.4 does not have this computation option). Note the option of TIES=DISCRETE should be specified for SAS procedure PROC PHREG.

A summary table (**Table 14.2.4**) will include the following.

- number (%) subjects with and without (censored) event from the left ureter and from the right ureter. This will allow each subject to be accounted once per treatment,
- Kaplan-Meier product limit estimates of quartiles of time to first event (25%, 50%, and 75% tiles and 95% CIs) and
- KM means (SE) of time to first event
- Hazard ratio (IC High/IC Low) and 95% Cis and p-value based on score test.

To compute the KM means and its standard error, in case a subject is censored at 10 minutes the option **TIMELIM** will be set to the maximum observed time in minutes when SAS procedure PROC LIFETEST is used to perform KM survival analysis. Hence, the calculated mean survival time will be the area under the Kaplan-Meier survival curve from 0 to this maximum observed time.

Below is an example of SAS syntax to estimate the difference between treatment groups IC High dose vs IC Lower dose using the external SAS macro HazardRatio. **This parameter will not applicable for Saline treatment.**

```
DATA CoxHS;
  set ttv;
  If CNSR=0 THEN EVENTYN=1;  *-- YES ---*;
  If CNSR=1 THEN EVENTYN=0;  *-- NO ---*;
  TIME=AVAL;
  if trt='IC High' then Treatment=1; else Treatment=0;
run;
```

⁴ Lin DY, Dai L, Cheng G, Sailer MO: On confidence intervals for the hazard ratio in randomized clinical trials. *Biometrics*, 75: 1098-1102, 2016. <http://dlin.web.unc.edu/software/HazardRatio/>

```
*---- use the macro to get Score HR 95% CI ****;
%HazardRatio (Data = CoxHS, Result=HR HL, Time = Time, Status =
EventYN, Ties=DISCRETE, Stratum = Ureter, Treatment = Treatment, Alpha
= 0.05, Accuracy = 0.00001);

data Result1;
    set HR_HL; if method='Score';
    HR=exp(estimate);
    HR_Lower=exp(Lower);
    HR_Upper=exp(Upper);
Run;
```

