5.5.3. Dichotomization of the Difference in Conspicuity

The third approach is to dichotomize the difference in conspicuity between the surgeon and the blinded reader. The four scores from the surgeon will be paired with the four scores from the blinded central reader based on treatment and ureter for a given subject. Based on the difference in the paired conspicuity (see [Section 3.8.5](#)) a concordance response variable will be derived for each pair of the conspicuity:

- a. the ratings are in agreement when the difference in score is (+1, 0, -1), otherwise
- b. the ratings are not in agreement when the difference is more than +/- 1 point

The association of this concordance response variable (agree vs not agree) with treatment and ureter will also be evaluated using the GEE model based on the concept of logistic regression for dichotomized response. In case of missing data that prevent from forming a pair of observations to derive this concordance response variable, the data will be excluded from this analysis.

The score statistics will be used to determine if the treatment is statistically associated with this dichotomized response. The following is an example of SAS syntax for this analysis between the IC Hight dose vs Saline. This analysis will be performed separately for each comparison (IC High dose vs Saline, IC Low dose vs Saline, and IC High dose vs IC Low dose). All subjects with ≥ 1 missing data from either surgeon or central reader will be excluded from this analysis.

```

PROC GENMOD DATA=dischotH descending;
CLASS usubjid ureter(ref='Right') TRT(ref='Saline');
MODEL response (event='Y') = trt ureter trt*ureter
                           /LINK=LOGIT DIST=BINOMIAL TYPE3; (Model 5)
REPEATED subject = usubjid / type=EXCH;
ESTIMATE 'OR: IC vs Saline' trt 1 -1 / exp;
Run;

```

```

PROC GENMOD DATA= dischotH descending;
CLASS usubjid ureter(ref='Right') TRT(ref='Saline');
MODEL response (event='Y') = trt ureter
                           /LINK=LOGIT DIST=BINOMIAL TYPE3; (Model 6)
REPEATED SUBJECT = usubjid / TYPE=EXCH;
ESTIMATE 'OR: IC vs Saline' trt 1 -1 / exp;

```

Where:

1. 'TRT' is coded to IC or Saline
2. 'URETER' is coded to 'Left' or 'Right'
3. 'USUBJID' is the unique Subject Identification
4. REPEATED statement controls the intra-subject correction due to repeated measures. In this example, exchangeable working correlation structure is used (TYPE=EXCH).

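### SAP 5.4 treats a subject's two ureters as independent in the time-to-visualization analysis, so any positive left-right correlation overstates the precision of the dose comparison and of the pooled Kaplan-Meier summary

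*SAP*

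**What the plan says.** SAP section 5.4 has each subject contribute two TTV observations, left and right, and then states: "Each time to event observation will be considered an independent observation".

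Three outputs follow from this:

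- **Kaplan-Meier summaries** by ureter, plus an overall summary that pools both ureters. For the overall summary the SAP notes that "In this analysis, number of observations will not be the same as number of subjects".
- **A Cox model** for High versus Low dose, stratified by ureter, fitted only if the data are judged to support it. The macro call reads "EventYN, Ties=DISCRETE, Stratum = Ureter, Treatment = Treatment, Alpha". It names the ureter stratum and no subject or cluster variable. The PROC LIFETEST code likewise stratifies by ureter without a subject identifier.
- **Table 14.2.4**, whose listed contents include "Hazard ratio (IC High/IC Low) and 95% Cis and p-value based on score test".

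Dose is randomized per subject (SAP section 2), so both ureters of a subject always carry the same dose. Elsewhere the SAP does respect this pairing. The conspicuity models in section 5.1 cluster on subject, and the concordance models in section 5.5.3 use "REPEATED subject = usubjid / type=EXCH".

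**The concern.** Stratifying by ureter lets the left and right baseline hazards differ. It does nothing about the dependence between two times from the same person: the score variances of the two strata are added as if they came from different people. Because dose varies only between subjects, the omitted covariance always acts in one direction when the correlation is positive, towards an understated variance.

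A positive correlation is plausible because the two ureters share one injection and one dose. The SAP gives no reason for treating the pairing differently here than for conspicuity and concordance.

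What is at stake is the stated precision of a secondary endpoint: the hazard-ratio interval and p-value in Table 14.2.4 if the Cox model is fitted, and the intervals and standard errors of the pooled Kaplan-Meier summary, which is planned unconditionally.

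**Working it through.** The documents give no event count, error rate or power for TTV, so there is no figure of the plan's own to reproduce.

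**Inputs from the SAP.** About 116 − 21 = 95 subjects for efficacy (sections 3.2 and 3.3), hence 2 × 95 = 190 TTV observations. Roughly equal dose groups (implied by section 3.7). Censoring at 10 minutes (section 3.8.3). Two-sided 95% interval (section 5.4).

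**Assumed.** The left-right correlation, and in the simulations also exponential times with a median of 5 or 8 minutes.

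**Formula.** The stratified score is U = U_left + U_right. Let each part have variance V, and let ρ be the correlation of the two parts.

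- Variance the model uses: V + V = 2V.
- True variance: 2V + 2ρV = 2V(1 + ρ).
- True SE / reported SE = √(1 + ρ).
- True error of a nominal 5% test = 2 × [1 − Φ(1.96/√(1 + ρ))].

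For ρ = 0.5: √1.5 = 1.22; 1.96/1.2247 = 1.600; the error is 11.0%, so the 95% interval covers about 89%. The 190 observations then carry the information of 190/1.5 ≈ 127.

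| ρ (score contributions) | 0 | 0.1 | 0.3 | 0.5 | 0.7 | 0.9 |
|---|---|---|---|---|---|---|
| SE excess | 0% | 5% | 14% | 22% | 30% | 38% |
| True type I error | 5.0% | 6.2% | 8.6% | 11.0% | 13.3% | 15.5% |

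**Simulation under no dose effect.** 8,000 replicates, 48 subjects per dose, paired exponential times from a Gaussian copula rounded up to the second, median 5 minutes (75% events). The correlation set here is the latent copula value; the score correlation it produces is somewhat lower. Monte Carlo error is about 0.2 to 0.4 percentage points.

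| Copula correlation | 0 | 0.1 | 0.3 | 0.5 | 0.7 | 0.9 |
|---|---|---|---|---|---|---|
| Resulting score correlation | 0.00 | 0.08 | 0.25 | 0.42 | 0.61 | 0.83 |
| Type I error, ureter-stratified test | 5.0% | 5.9% | 9.0% | 9.9% | 12.5% | 15.2% |
| SE excess of the score | 0% | 3% | 14% | 18% | 26% | 37% |
| Pooled Kaplan-Meier SE excess | 2% | 3% | 11% | 15% | 23% | 32% |

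A score test clustered on subject held 5.2 to 6.0% in the same runs. With a median of 8 minutes (58% events) the unclustered test ran from 5.2 to 15.1% and the clustered test from 4.7 to 5.6%.

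A separate simulation (6,000 replicates, 48 and 47 subjects, untied times, median 5 minutes) gave 5.0, 7.5, 10.4, 11.6 and 14.6% at copula correlations 0, 0.3, 0.5, 0.7 and 0.9. The 9.0% at 0.3 in the table is therefore slightly high; the formula at score correlation 0.25 gives 8.0%.

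**Pooled Kaplan-Meier.** The quantity checked is survival at the true median in one dose group, against the Greenwood SE. The 2% at zero correlation is baseline noise, not clustering. As a cross-check, the event indicators at the median correlate at (2/π)·arcsin(copula correlation). At 0.5 this is 1/3, so the SE ratio is √(4/3) = 1.155, matching the simulated 15%. For one ureter alone the ratio stayed between 0.985 and 1.023, so the per-ureter summaries are sound.

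**The case against.** The strongest counter-argument is about weight. The TTV objective is descriptive and the dose comparison exploratory (section 2), the Cox model is optional (section 5.4), and type I error control covers conspicuity only (section 3.4). No decision uses the hazard ratio, the per-ureter summaries are valid, and the SAP states its assumption openly. All of this is correct and limits the importance of the point. It does not make an interval labelled 95% correct, and the pooled Kaplan-Meier summary is not optional.

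Second, the correlation is unknown, and nothing in the documents supports a value as high as 0.9. That stands: the upper end of the tables is not an expectation. Alternating filming of the two ureters (section 2) could weaken the correlation. The rule in section 3.8.3.1 for a ureter with an initial problem could go either way: weaker if only that ureter is censored, stronger if the whole subject is, as its wording suggests.

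Third, the Kaplan-Meier check concerns survival at the median, not the quartile intervals or the mean that Table 14.2.4 will show. The direction carries over, but the exact size may differ.

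Fourth, changing the ties method goes beyond the defect. This is partly fair: it is needed only if the software cannot combine discrete ties handling with a clustered variance.

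**Conclusion.** The concern holds. The independence assumption is explicit, the code implements it, and the same SAP clusters the same pairing elsewhere. With positive left-right correlation, the hazard-ratio interval is too narrow, its p-value is too small on average, and the pooled Kaplan-Meier errors are too small. For score correlations of 0.1 to 0.9, the true SE of the log hazard ratio is 5 to 38% above the reported one and the true error of a 5% test is 6.2 to 15.5%. With zero correlation nothing is wrong.

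The size rests on an assumed correlation; the direction needs only that it be positive. The unclustered variance does not bias the hazard-ratio or Kaplan-Meier point estimates. The point should be fixed, but it does not threaten the trial's main conclusion.

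**What to change.** Delete the independence sentence in section 5.4 and put in its place:

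> *The left and right TTV of a subject are paired observations. If fitted, the Cox model will be stratified by ureter, and the hazard-ratio 95% CI and p-value will use a sandwich variance clustered on USUBJID.*

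In SAS this is PROC PHREG with COVS(AGGREGATE), ID USUBJID and STRATA URETER. If a score p-value is preferred, name the subject-clustered score test in advance, so that the source of the p-value is not left open.

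Three consequential edits:

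- The SAP says "Note the option of TIES=DISCRETE should be specified for SAS procedure PROC PHREG". If the software does not offer the clustered variance with that option, state a ties method that does work with it, for example Efron.
- Remove the statement that the p-value will equal that of the stratified log-rank test, and do not report an unclustered log-rank p-value for the dose comparison.
- For the overall Kaplan-Meier quartiles and means, use a subject-level bootstrap or cluster-robust intervals, or report by ureter only.

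The cost is SAP wording and a few lines of code, and the external score-interval macro is no longer needed. With positive correlation, intervals widen by about √(1 + ρ). A different ties method could move the hazard ratio slightly where times are tied to the second. The clustered score test can run a little above 5% (up to 6.0% in the simulation).
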